	2.6.	5 Survival analysis13
	2.6.	6 Causes of death13
	2.7	Subgroups
	2.8	Bayley-III and ASQ-3 calibration sub-study14
A	ppendi	(One

Version number	Changes	Author
1 (May 2019)	Initial draft prepared by [name] and reviewed by [name]	[name]
2 (July 2019)	Updates to incorporate inputs from [name]	[name]
2.1 (June 2020)	Updates to include treatment adherence weighted analysis	[name]
2.2 (August 2020)	Updates to include additional treatment adherence weighted analysis and multiple imputation analysis	[name]/[name]

August 2020

Page 2 of 17

Page 66 of 81

APTS FU Statistical Analysis Plan v2.2

1 SYNOPSIS

1.1 Primary clinical hypothesis:

An autologous transfusion of placental blood at birth will improve health outcomes in preterm babies born less than 30 weeks.

1.2 Study design:

This is a multicentre 2-arm parallel open label randomised controlled trial

1.3 Study interventions:

The two arms of the trial comprise:

- early cord clamping (which is the control arm) is clamping the cord within 10 secs of birth
- delayed cord clamping (for 60 seconds or more with the baby held below or at the level of the placenta)

1.4 Outcomes for the follow-up study:

Primary outcome Death and/or major disability at 24 months

Secondary outcomes Incidence of the following outcomes at 24 months:

- 1. Death
- 2. Major disability
- 3. Components of major disability
- 4. ASQ domain scores

1.5 Power and Sample Size

Infants recruited into the main APTS study are expected to complete extended follow-up. Assuming that, at most, 150 infants will be lost or not followed to two years, the table below gives an estimate for the absolute difference between the interventions that could be detected for a range of sample sizes and event rates for the primary endpoint allowing for 30% non-compliance. The absolute reduction that could be detected maintaining 80% power is shown.

Table 1: Long term follow-up scenarios for absolute difference that could be detected for possible sample sizes

Secondary endpoint	Sample Size	Absolute difference	Power
Mortality and major disability	1350	10% (35% to 25%)	80
up to 36 months	1400	9.8% (35% to 25.2%)	80
	1450	9.6% (35% to 25.4%)	80
	1350	10.3% (40% to 29.7%)	80
	1400	10.2% (40% to 29.8%)	80
	1450	10% (40% to 30%)	80

1.6 Subgroups

The following subgroups will be investigated for evidence of a difference in the treatment effect on death or major disability at 24 months: gender and gestational age (<27 weeks vs \geq 27 weeks).

August 2020

Page 3 of 17

Page 67 of 81

[figure not shown]
APTS FU Statistical Analysis Plan v2.2

2 STATISTICAL ANALYSIS

The primary analyses will be performed on assigned treatment. As randomisation occurs when birth is imminent, occasionally babies are not born immediately following randomisation. Babies that are stillborn or born after 30 weeks gestation are not to be included in the intention to treat population.

As consent for the babies recruited into the pilot APTS study did not include collection of follow-up data, these pilot babies are not included in the APTS FU study (n=35).

P-values less than 0.05 will be considered statistically significant and there will be no adjustments for multiple comparisons.

Page 4 of 17

Page 68 of 81

APTS FU Statistical Analysis Plan v2.2

2.2 Follow-up cohort

Table 2: Children with follow-up data available

	Immediate cord clamping	Delayed cord clamping					
Total babies randomised	816	818					
Babies not included in ITT							
 Ineligible babies (born >30 weeks) 	27	27					
• Withdrawn consent (prior to delivery)	2	2					
Stillborn babies	5	5					
Babies included in main study ITT	782	784					
Babies removed because included in the pilot study							
Babies available for the APTS Followup study							
No follow-up obtained	No follow-up obtained						
Partial follow-up obtained, but incomplete							
Data available for primary outcome at 24 months							

2.3 Treatment adherence in FU cohort

Table 3: Summary of overall treatment adherence by treatment

Variable	Immediate cord clamping	Delayed cord clamping
Babies in intention to treat population		
Not as randomised, intervention received will never be known !		
Not as randomised (>10sec for ICC , <60sec for DCC, milking in either arm)		
As randomised		
(\leq 10sec for ICC, \geq 60sec for DCC, no milking in either arm)		
IThese babies include babies that were that withdrew con information has not been recorded.	nsent, transferre	ed prior to delivery

Page 5 of 17

Page 69 of 81

APTS FU Statistical Analysis Plan v2.2

2.4 Delivery and admission characteristics in FU cohort

We will also compare the baseline characteristics of those that are in the FU cohort compared to those that are not in the FU cohort.

Table 4: Patient characteristics at admission and delivery by treatment

	Immediate Cord Clamping Delayed Cord Clampin
N	
Males	
Gestational Age (weeks)*	
Babies <27 weeks gestation*	
Birth details	
Mode of delivery	Vaginal with instruments
	Vaginal without instruments
	Caesarean in labour
	Caesarean not in labour
Presentation at birth	Cephalic
	Breech
	Other (including transverse)
	Unknown
Infants of multiple births	Singletons
(only counting births in the ITT population)	Twins
	Triplets
	Quadruplets
Maternal assessment	
Ethnicity	Caucasian
	Aboriginal/TSI
	Asian
	Pacific Islander & Maori
	Africanŧ
Variables collected pre and po	ost intervention
Uterotonic agents administered	
If yes, what agent?	Syntocin
	Ergometrine
	Carbetocin
	Syntometrin
	Other (including multiple agents)
If yes, what route?	IV
	IM
If yes, timing?	Pre-clamping
	Post-clamping

All characteristics measured prior to intervention were p>0.xx.

*Gestational age is gestational age at birth, as originally specified by the site. Note that reassessed GA has not been used.

+ includes African American. Statistics are given as N (%), mean (SD) or median (Q1-Q3).

August 2020

Page 6 of 17

Page 70 of 81

APTS FU Statistical Analysis Plan v2.2

2.5 Outcome definitions

The primary outcome is death and/or major disability at 24 months corrected age. Assessments of major disability must be performed between 18 months to 27 months. Any data outside of this window will require a central review.

2.5.1 Definition of death

The survival data will be used up to 24 months corrected age. Only babies who are known to be alive at 21 months corrected or later will be deemed as 'alive' at 24 months. Deaths after 24 months are not included.

2.5.2 Definition of major disability

Follow-up assessments should be performed on all APTS babies eligible for follow-up using the short health status questionnaire (SHSQ) and the Ages and Stages Questionnaire (ASQ-3). Additionally, some sites routinely use the Bayley scales of Infant and Toddler Development – Third edition (Bayley-III) which has been collected where available.

Major disability is defined by one or more of the following:

- Cerebral palsy with an inability to walk unassisted at or after 2 years corrected age,
- Severe visual loss (legally blind i.e. corrected acuity <6/60 in both eyes),
- Deafness, requiring a hearing aid or cochlear implants,
- Major problems with language or speech at or after 2 years corrected for gestation defined by the inability to use more than 10 words (including signed words)
- Cognitive delay as defined below.

A tiered approach (Table 2) will be used in order to obtain a disability status for as many babies as possible. If the data is not available for Tier 1, the disability status will be obtained from Tier 2, otherwise Tier 3. A central review blinded to treatment will be performed as appropriate and all of the information available at any time (i.e. Bayley-III) will be reviewed. If the outcome for an infant is not available from tier 1 or 2 results and can then not be ascertained with a central review, the primary outcome for this infant will be missing.

August 2020

Page 7 of 17

Page 71 of 81

APTS FU Statistical Analysis Plan v2.2

Table 5: Identification of major disability⁺

Disability type	Tiers to move through in order to determine disability status	Definition of Disability present within each tier	Definition of Disability absent within each tier
Cerebral palsy	Tier 1: SHSQ competed after 22 months.	'CP = Yes' and the inability to walk unassisted	'CP = No' or 'CP=Yes' but only an unsteady walk
	Tier 2: ASQ-3 completed after 18 months	Score of 0 for Gross Motor domain	Score >0 for gross motor domain
	Tier 3: Central review required		
Severe visual loss	Tier 1: SHSQ completed at any age	Legally blind = Yes	Legally blind = No
	Tier 2: Central review required		
Deafness	Tier 1: SHSQ completed at any age	Hearing loss = Yes with requirement for hearing aids	Hearing loss = No or Hearing loss = Yes with no requirement for hearing aids
	Tier 2: Central review required		
Major problems with language or speech	Tier 1: SHSQ completed between 22-27 months (inclusive)	Unable to speak 10 words	Able to speak >10 words
	Tier 2: ASQ-3 completed after 18 months	Communication score indicative of delay (based on published ASQ cut-off)	Communication score not indicative of delay (based on published ASQ cut-off)
	Tier 3: Central review		
Cognitive delay	Tier 1: ASQ-3 completed after 18 months	Problem solving score indicative of delay (based on published ASQ cut-off)	Problem solving score not indicative of delay (based on published ASQ cut-off)
	Tier 2: Central review		

⁺ the windows given above for the determination of disability using the various sources were determined by clinicians involved in the APTS Follow-up study. All ages are corrected ages.

If the baby is alive and does not have one of the above major disabilities, and has been assessed for all of the above components, then they will be classified as alive and disability free. If the infant was alive and has no disability for CP, severe visual loss, deafness and major problems with language or speech, but missing information for cognitive delay, then the infant will be assumed to be alive and disability free at 2 years. Otherwise the infant will be considered as missing for the primary analysis.

Page 8 of 17

Page 72 of 81

APTS FU Statistical Analysis Plan v2.2

Table 6: Summary of completeness of the primary outcome and its components

Endpoint	Complete data	Missing data
Death or disability at 24 months		
Death status		
Cerebral palsy ⁺		
Severe visual loss+		
Deafness [†]		
Major problems with language or speech ⁺		
Cognitive delay ⁺		
hese analyses are restricted to those that were as	ssessed for these outcon	nes

Additionally, the baseline characteristics will be compared between those that have outcome data at 24 months versus those that have missing data at 24 months.

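### SAP Table 5, which assigns disability status for the primary outcome, does not implement the definition of major disability in the same section

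*Supplement*

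**What the plan says.** Section 2.5.2 of the SAP lists five components, any one of which makes a major disability. Three matter here.

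- Deafness: "Deafness, requiring a hearing aid or cochlear implants".
- Cerebral palsy: "Cerebral palsy with an inability to walk unassisted at or after 2 years corrected age".
- Language or speech: a major problem at or after 2 years corrected age, "defined by the inability to use more than 10 words (including signed words").

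Table 5 then assigns each component by tiers. A later tier is used only if the earlier one has no data.

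- Deafness, Tier 1 (short health status questionnaire, SHSQ, at any age): present is "Hearing loss = Yes with requirement for hearing aids". Absent is no hearing loss, or "Hearing loss = Yes with no requirement for hearing aids".
- Cerebral palsy, Tier 1 (SHSQ after 22 months): present is "CP = Yes' and the inability to walk unassisted". Tier 2 (ASQ-3 after 18 months): a gross motor score of 0 is present, and "Score >0 for gross motor domain" is absent. Tier 3 is central review.
- Language, "Tier 1: SHSQ completed between 22-27 months (inclusive"): one cell holds children who cannot speak 10 words, the other those who speak more than 10. Tier 2 is the ASQ-3 communication score after 18 months, against the published cut-off. Tier 3 is central review.

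Two further rules bear on this. Section 2.5 sets an assessment window of 18 to 27 months and requires central review of data outside it. Section 2.5.2 provides a review blinded to treatment where appropriate, drawing on all information available at any time.

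**The concern.** Table 5 is the rule that a programmer would code, while the bulleted definition is what the trial says it measures. If they differ, two competent programmers can build different primary-outcome datasets from the same forms.

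The components are also reported in their own right. Section 2.6.1 allows a formal analysis of a component only with more than 10 events in each arm. In an arm with 11 true events, one miscoded child gives 11 − 1 = 10, which fails the rule. A handful of children could therefore decide whether cerebral palsy or deafness is tested at all.

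A wrong absent code can also carry through to the composite. A survivor coded absent on cerebral palsy, vision, deafness and language, but with cognition missing, is assumed to be disability free.

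**Working it through.** **Step 1: definition against table.** Each row is one type of child.

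| Child | Definition (2.5.2) | Table 5 |
|---|---|---|
| Hearing aid | event | present |
| Cochlear implants, no hearing aid, SHSQ available | event | absent at Tier 1; review tier not reached |
| 9 words, all spoken | event | present |
| Exactly 10 words, all spoken | event | neither cell |
| 11 words, all spoken | no event | absent |
| More than 10 words only if signs are counted | no event | not absent; present if fewer than 10 are spoken |
| Cerebral palsy, not walking, SHSQ at or after 24 months | event | present |
| SHSQ at 20 months records cerebral palsy, ASQ-3 gross motor above 0 | not settled by a 20-month form | absent at Tier 2 |
| No cerebral palsy, no SHSQ after 22 months, gross motor score 0 | no event | present at Tier 2 |
| SHSQ at 29 months with too few words, ASQ-3 at 19 months not indicating delay | event | tier rule: absent; section 2.5: central review |

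The language rows assume an SHSQ between 24 and 27 months unless stated.

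Three things follow.

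- The deafness fault sits in Tier 1, so it applies to every child with an SHSQ.
- The Tier 1 language fault is a gap at exactly 10 words plus the loss of signed words. It does not code a child who meets the definition as absent.
- The cerebral palsy and late-language faults arise only in the ASQ-3 fallback.

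The 20-month case lies inside the 18 to 27 month window, so section 2.5 does not compel review. The 29-month case lies outside the window, so section 2.5 does compel it, but the tier rule points to the earlier ASQ-3. Table 5 itself accepts an SHSQ at any age for vision and deafness, so the reader cannot assume that the window governs every row.

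Table 5 also accepts an SHSQ from 22 months for cerebral palsy and language. It can therefore record an event before the age of 2 years set in the definition.

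**Step 2: what a given error rate would do to the composite.** The documents give no component rates, so this is an illustration.

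Inputs from SAP section 1.5, Table 1: N = 1350, 35% against 25%, 30% non-compliance, 80% power. Assumed: 1:1 allocation, two-sided 0.05, all dilution in the deferred arm.

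Diluted difference = 10 × 0.7 = 7 points, so 35% against 28%, with n = 675 per arm.

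Power = Φ{[|p1 − p2| − 1.96√(2p̄(1 − p̄)/n)] / √[(p1(1 − p1) + p2(1 − p2))/n]} = 79.1%, which reproduces the stated 80%. Splitting the dilution equally between the arms gives 80.2%.

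*Missed events.* Assume that deaths make up 8 points of the control 35% and, in proportion, 0.08 × 0.28/0.35 = 6.4 points of the 28%. Assume also that a fraction f of disability events is missed equally in both arms. The rates become 0.08 + 0.27(1 − f) and 0.064 + 0.216(1 − f).

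| f | Rates | RR | Power | Children missed |
|---|---|---|---|---|
| 1% | 34.73% v 27.78% | 0.80 | 78.7% | 1.8 + 1.5 |
| 5% | 33.65% v 26.92% | 0.80 | 76.8% | 9.1 + 7.3 |
| 10% | 32.30% v 25.84% | 0.80 | 74.4% | 18.2 + 14.6 |

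*False events.* If 1% of true non-events are coded present, the rates are 35.65% and 28.72%, RR 0.806, power 77.9%. At 2% the RR is 0.811 and power 76.6%.

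**The case against.** The strongest reply is that these are loose ends in wording.

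- **Deafness.** The SHSQ form is not shown. The protocol (V4.0, section 3.4.4) describes the questionnaire as documenting deafness that needs an aid or an implant, so Table 5 may be using shorthand for one combined item. That is possible, but the analysis plan should not depend on it: Table 5 names only aids, and its absent cell is explicit.
- **Cerebral palsy.** The definition applies at or after 2 years, so keeping a 20-month SHSQ out of Tier 1 is consistent with it. The documents do not say that a non-walking child can score above 0. A reader might infer that such a child is a true event turned into a non-event, but the documents do not establish that. What stands is that the fallback measures neither element of the definition and can overrule a recorded diagnosis with no required review.
- **Language after 27 months.** A reader might infer that the child seen at 29 months is simply coded absent. Section 2.5 already requires review of out-of-window data, so that is too strong. What stands is that two rules conflict and the SAP does not say which prevails.
- **Blinded review.** It is available where appropriate, so review is not ruled out. But it is discretionary, and no trigger is named for sources that disagree.
- **Composite.** A missed component changes the primary outcome only if the child has no other qualifying component. This is correct and limits the effect.

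**Conclusion.** Table 5 contradicts the definition it is meant to apply, and it should be reconciled. The clearest fault is the omission of cochlear implants at Tier 1. Next come the missing cell at exactly 10 words and the loss of signed words. The ASQ-3 fallbacks are a weaker but real problem, because they do not measure the defined conditions and their relation to central review is unclear.

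A reader might infer that the table systematically loses true events from the primary outcome. The documents do not support that. Some rules miss events, while others create them (gross motor 0 without cerebral palsy, signed words ignored, forms completed before 2 years). The net direction is not established.

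The number of affected children cannot be computed, because the documents give no rates for implants, non-walking cerebral palsy or missing late questionnaires. The effect on the composite is probably small: in the illustration, missing 1% of disability events costs 0.4 points of power (79.1% to 78.7%) and leaves the relative risk unchanged. That result assumes equal error in both arms. The consequence is larger for the cerebral palsy and deafness components, because of the rule of more than 10 events per arm.

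**What to change.** Amend Table 5, blinded to allocation, as follows.

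1. Deafness present: hearing loss requiring hearing aids or cochlear implants. Absent: no hearing loss, or hearing loss requiring neither.
2. Language, Tier 1, present: unable to use more than 10 words, spoken or signed. Absent: able to use more than 10. Every count then has a cell.
3. Any child whose SHSQ records cerebral palsy but fails the Tier 1 age rule, or whose SHSQ after 27 months shows too few words, goes to the existing blinded central review before an ASQ-3 result can code that component absent.

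The gross motor threshold need not move. Replacing 0 with the published cut-off would be a design choice, since that cut-off identifies delay rather than non-walking cerebral palsy. While the section is open, correct the reference to Table 2 for the tiers, which are in Table 5.

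The cost is SAP wording and some additional blinded reviews, whose number cannot be given from the documents. No new data are needed.

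### Survivors whose cognition stays unknown after central review are coded as certain non-events in the primary outcome, and no planned analysis tests that assumption

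*Supplement*

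**What the plan says.** All references are to the follow-up SAP v2.2.

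- Section 2.5.2 lists five criteria, any one of which makes a major disability. The last is "Cognitive delay as defined below".
- The tier paragraph of 2.5.2 gives the general rule: "If the outcome for an infant is not available from tier 1 or 2 results and can then not be ascertained with a central review", then "the primary outcome for this infant will be missing". It states no exception.
- Table 5 takes cognition from the ASQ-3 problem-solving score after 18 months and, failing that, from central review. The review is blinded to treatment and may use any available information, including Bayley-III. The short health status questionnaire has no tier for cognition.
- Below Table 5, a survivor without any of the disabilities who "has been assessed for all of the above components, then they will be classified as alive and disability free". The next sentence covers a survivor clear on cerebral palsy, vision, hearing and language "but missing information for cognitive delay, then the infant will be assumed to be alive and disability free at 2 years". Children who fit neither description are missing for the primary analysis.
- Section 2.6.4 plans multiple imputation of the primary outcome as a sensitivity analysis. Its covariates are treatment, gestational age, sex, birthweight, multiple birth and mode of delivery. No disability component is among them.

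**The concern.** A child who is clear on four components and unknown on the fifth has an unknown composite. The SAP records that child as a known non-event. The general rule in the tier paragraph would make the same child missing, and neither sentence refers to the other.

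The coding carries through the plan. These children are not missing for 2.6.4, so the only missing-data analysis leaves them as they are. The adjusted (2.6.2), adherence-weighted (2.6.3) and subgroup (2.7) analyses use the same coding. The cognitive-delay row of Table 7 is restricted to children assessed for it, so one child can be outside that denominator and still be a non-event in the primary row.

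At stake are the level of the event rate and, if unresolved cognition is more common in one arm, the relative risk. The trial is open label and the ASQ is completed by parents, so equal return in both arms cannot be taken for granted.

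**Working it through.** **The SAP's own figure first.** SAP Table 1, first row: N = 1350, 35% to 25%, 30% non-compliance, 80% power. Diluting the 10-point difference by 0.70 gives 35% against 28%. With a pooled-variance test at two-sided 0.05 and 1:1 allocation, power is 0.791 if all the non-compliance is in the deferred arm, and 0.802 if it is split 15%/15% (33.5% against 26.5%). The stated 80% reproduces, so no sample-size figure is in question.

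**Notation.** For one arm:
- p = true event rate.
- c = share of infants whose only event is cognitive delay.
- f = share of survivors clear on the other four components whose cognition is still unknown after review.

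None of these is in the documents as an observed figure; f and c are assumed ranges. One anchor for c is the 2014 follow-up application, which assumes a 20% event rate when sizing its ASQ/Bayley-III calibration sample. If 25-75% of that were isolated, c would be 5-15%. If missingness is unrelated to the child's true cognition, then

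observed rate under the SAP rule = p − f·c.

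**Equal missingness.** At f = 10% and c = 5-15%, the rate is understated by 0.10 × 0.05 = 0.5 to 0.10 × 0.15 = 1.5 percentage points. For the relative risk, take 35% against 28% (RR 0.80), deaths 10% against 8%, and cognitive-only delay as 25-50% of disability events:
- f = 5%, 25% cognitive-only: 0.35 − 0.05 × 0.0625 = 0.347; 0.28 − 0.05 × 0.05 = 0.2775; RR 0.80; power 0.786.
- f = 20%, 50% cognitive-only: 0.35 − 0.20 × 0.125 = 0.325; 0.28 − 0.20 × 0.10 = 0.260; RR 0.80; power 0.748.

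The relative risk holds, and power falls from 0.79 to between 0.79 and 0.75.

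**Unequal missingness, no true effect.** p = 30% in both arms; f = 15% in one arm and 5% in the other. The last column shows what happens if these children are dropped instead. The observed rate is then (p − f·c) / [1 − f(1 − (p − c))], because only children clear on the other four components leave the denominator.

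| c | SAP rule, RR (arm with 15% missing / arm with 5%) | Dropped instead, RR |
|---|---|---|
| 5% | 0.2925/0.2975 = 0.983 | 0.3296/0.3091 = 1.066 |
| 10% | 0.2850/0.2950 = 0.966 | 0.3239/0.3073 = 1.054 |
| 15% | 0.2775/0.2925 = 0.949 | 0.3180/0.3055 = 1.041 |

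With the arms reversed, the SAP rule gives 1.017, 1.035 and 1.054. At 675 per arm the shift is about 0.2 to 0.6 standard errors, so the two-sided type I error would be about 5.5-9.4% instead of 5% (independent observations assumed).

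**Dropping with equal missingness.** At p = 35% and f = 10%:
- c = 5%: SAP rule 34.5%; dropped 0.345/0.93 = 37.1%.
- c = 15%: SAP rule 33.5%; dropped 0.335/0.92 = 36.4%.

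Dropping overstates the rate because it removes non-events while keeping every child already positive on another component.

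**The case against.** The strongest reply has four parts.

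**The rule bites late.** A reader might infer that any child without an ASQ-3 is set to no delay. Table 5 does not say that: central review comes first and may draw on Bayley-III. The child must also be clear on the other four components, so a child with neither form stays missing unless review settles the matter. This stands. It means f is smaller than the share without an ASQ-3, and the 5% and 15% used above may be too high.

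**The text can be read consistently.** A reader might infer a flat contradiction. The sentence below Table 5 is the more specific one, and it is followed by a sentence making all remaining patterns missing, so it reads as an exception to the general rule. This largely stands. What is lacking is a cross-reference and a reason for the exception.

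**The effect on the relative risk is conditional.** A reader might infer that the treatment estimate is biased. The documents do not show this: with equal missingness it is nearly preserved, and there is no evidence that missingness differs by arm. Tables 6 and 7 would also disclose how complete the cognitive data are. That stands, but disclosure does not re-run the composite under another assumption.

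**The survival rule.** A reader might also infer an opposite asymmetry, because 2.5 says "Assessments of major disability must be performed between 18 months to 27 months" while 2.5.1 says "Only babies who are known to be alive at 21 months corrected or later will be deemed as" alive at 24 months. The SAP does not state how a child found disabled at 18-20 months with unknown later survival is coded, and 2.5.1 requires knowledge of survival, which any later contact supplies. That inference is not part of this point.

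**Conclusion.** The concern holds in a limited form. SAP 2.5.2 turns an unknown cognitive result into a certain non-event for survivors clear on the other four components once review has failed, and no planned analysis varies that choice. With equal missingness the consequence is small: an event rate too low by about 0.5-1.5 points at 10% missing, and a relative risk nearly unchanged. With an assumed 10-point difference between arms, a null relative risk moves by about 2-5%, towards apparent benefit for the arm with more missing data.

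These sizes rest on assumed values of f and c, and on missingness unrelated to the child's true state. If delayed children are the ones more often unresolved, the loss is larger than f·c. The documents support saying that the plan cannot detect or bound the effect. They do not support saying that the result is biased.

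**What to change.** 1. In 2.6.4, treat the cognitive component of these children as missing and impute it at component level. Add the other disability components and in-hospital morbidity to the imputation model, then derive the composite in each imputed data set.
2. Report this beside the result under the present rule. Alternatively, make it the primary analysis and keep the present rule as the sensitivity analysis.
3. Do not simply set these children to missing in a complete-case primary analysis. On the inputs above, that gives a null relative risk of 1.04-1.07 against 0.95-0.98 under the present rule.
4. State in the tier paragraph of 2.5.2 that the sentence below Table 5 is an exception to the general rule, and give the reason.

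The cost is SAP wording and a little extra analysis. No new data are needed beyond what the follow-up study and the main trial already collect.
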